4.11. Hypothesis Testing and Multiple Comparisons

4.11.1. Primary Endpoint

In this single-arm study, hypothesis testing for the primary endpoint of ORR is performed using a confidence interval approach. Instead of reporting a p-value, 95% CI will be reported. Multiple comparison is not applicable.

4.11.2. Secondary Endpoints

The secondary endpoints of DOR, GCIG CA-125 response rate, PFS, and OS will be evaluated to further characterize the efficacy of MIRV. No formal hypothesis testing will be performed on secondary endpoints.

4.12. Analysis Populations

Seven analysis populations will be defined for use with various analyses. **Table 2** illustrates the relationship between each population and the analyses for which the data from the population will be used. **Table 2: Analysis Populations**

Analysis Population	Analysis				
	Reason for screen failure	Baseline	Patient Disposition	Efficacy	Safety
Screened	X				
Safety		X	X		X
Efficacy Evaluable by INV				X	
Efficacy evaluable by BICR				x	
CA-125 Evaluable				CA-125 only	
Per protocol				x	
ADA Evaluable				x	x

4.12.1. Screened

The Screened population includes all patients entered into the clinical database who have signed an informed consent.

4.12.2. Safety Population

All patients who received at least 1 dose of MIRV will be included in the Safety population.

4.12.3. Efficacy Evaluable Populations

The Efficacy Evaluable populations, per INV and BICR respectively, are defined as all patients in the Safety population who have measurable disease at baseline per INV/BICR assessments.

- Efficacy evaluable population for efficacy measurements based on Investigator's assessment (ORR, DOR, PFS per Investigator): this population includes all patients in the safety population who have measurable disease at baseline per Investigator.
- Efficacy evaluable population for efficacy measurements based on BICR assessment (ORR, DOR, PFS per BICR): this population includes all patients in the safety population who have measurable disease at baseline per BICR.

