The optimal two-stage design to test the null hypothesis that the ORR is \leq 28% versus the alternative that the ORR is \geq 48%, has an expected sample size of 37.74, and a probability of early termination of 0.762. If the ORR is \leq 28%, there is a 0.024 probability of rejecting the null hypothesis (the target 1-sided alpha value was 0.025). If the ORR is \geq 48%, there is a 0.9 probability of rejecting the null hypothesis. After testing the drug on 28 efficacy evaluable patients in the first stage, the study will be terminated for futility if 9 or fewer patients respond. If the study goes on to the second stage, a total of 69 efficacy evaluable patients will be enrolled. If the total number responding is more than 26, the null hypothesis is rejected. A total of approximately 75 patients will be enrolled to achieve 69 efficacy evaluable patients.

Study Eligibility

Inclusion Criteria

1. Patients \geq 18 years of age
2. Patients must have an Eastern Cooperative Oncology Group Performance Status (ECOG PS) of 0 or 1
3. Patients must have a confirmed diagnosis of high-grade serous EOC, primary peritoneal cancer, or fallopian tube cancer
4. Patients must have platinum-sensitive disease defined as radiographic progression greater than 6 months from last dose of most recent platinum therapy
Note: Progression should be calculated from the date of the last administered dose of platinum therapy to the date of the radiographic imaging showing progression
5. Patients must have progressed radiographically on or after their most recent line of anticancer therapy

6. Patients must have at least 1 lesion that meets the definition of measurable disease by RECIST v1.1 (radiologically measured by the Investigator)
7. Patients must be willing to provide an archival tumor tissue block or slides, or undergo procedure to obtain a new biopsy using a low-risk, medically routine procedure for immunohistochemistry (IHC) confirmation of FR α positivity
8. Patient's tumor must be positive for FR α expression as defined by the Ventana FOLR1 Assay
9. Prior anticancer therapy
 - a. Patients must have received at least 2 prior systemic lines of platinum therapy and be considered by the Investigator as appropriate for single-agent non-platinum therapy (documentation required – eg, high risk of hypersensitivity reaction; risk of further cumulative toxicity with additional platinum, including but not limited to myelosuppression, neuropathy, renal insufficiency or other)

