10. STATISTICAL METHODS

This is a Phase 2 study designed to evaluate the ORR of MIRV in patients with high FR α expressing, high-grade serous rPSOC.

All patients who have received at least 1 dose of MIRV will comprise the Safety Analysis Population.

The Efficacy Evaluable Population will include all patients who have received at least 1 dose of MIRV and have measurable lesions at baseline (per RECIST v1.1). The primary efficacy analysis of ORR and all other efficacy analyses will be based on the Efficacy Evaluable Population.

The safety analyses will be based on Safety Analysis Population.

All statistical analyses will be performed using SAS statistical software Version 9.4 or later, unless otherwise noted. For categorical variables, the number (n) and percent of each category within a parameter will be presented. For continuous variables, the sample size (n), mean, median, and standard deviation, as well as the minimum and maximum values, will be presented. Missing data will not be imputed unless otherwise stated. There will be a detailed description of patient disposition, patient demographics, and baseline characteristics.

A SAP will fully describe the planned analyses for this trial and will be finalized prior to database lock.

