6.1.1.1. ORR

The ORR will be calculated as the number of patients with a confirmed BOR of CR or PR divided by the number of patients in the Efficacy Evaluable population. Patients without at least 1 post-baseline RECIST assessment will be treated as non-responders (i.e., these patients will contribute to the denominator, but not the numerator).

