6.5. Additional Sensitivity Analyses

Analysis of ORR, DOR, and PFS as assessed by BICR will be performed as sensitivity analysis using the same methods described in the previous sections.

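### The BICR sensitivity analysis of ORR changes the patient set as well as the reader, so it likely understates Investigator-BICR disagreement

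*SAP*

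**What the plan says.** SAP 4.12.3 defines two Efficacy Evaluable populations, each starting from treated patients. For Investigator-read endpoints, "this population includes all patients in the safety population who have measurable disease at baseline per Investigator". For BICR-read ORR, DOR and PFS, "this population includes all patients in the safety population who have measurable disease at baseline per BICR".

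SAP 6.1.1.1 computes ORR as confirmed responders "divided by the number of patients in the Efficacy Evaluable population". Its one non-responder rule reads: "Patients without at least 1 post-baseline RECIST assessment will be treated as non-responders". SAP 6.5 carries this over to central review: "Analysis of ORR, DOR, and PFS as assessed by BICR will be performed as sensitivity analysis using the same methods described in the previous sections".

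At entry, measurability is the Investigator's call (Protocol Synopsis, inclusion criterion 6): "Patients must have at least 1 lesion that meets the definition of measurable disease by RECIST v1.1 (radiologically measured by the Investigator". Protocol Section 10 describes a single population: "The primary efficacy analysis of ORR and all other efficacy analyses will be based on the Efficacy Evaluable Population". Protocol 10.3 lets the SAP depart from that. SAP Section 9, which lists revisions from the protocol, records only the change from 4 to 6 post-baseline assessments.

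Protocol 7.13.1 gives the purpose of BICR as a sensitivity analysis of the Investigator's ORR, DOR and PFS. Neither document plans an Investigator-by-BICR concordance table, or a BICR ORR on the Investigator-evaluable set.

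**The concern.** The trial is open-label and single-arm, and its primary endpoint is read by the Investigator. BICR is the only independent reading of the scans. To work as a check, it should hold the patients fixed and change the reader. Here both change, so neither a difference between the two ORRs nor the lack of one can be put down to the reader.

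The patients who drop out are not a random subset. They are those on whom the two readers disagreed about baseline measurability, which is itself reader discordance. If the Investigator also called such a patient a responder, the comparison loses a clear example of what it is meant to show. The non-responder rule in SAP 6.1.1.1 does not bring her back, because it covers only patients with no post-baseline assessment.

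What is at stake is how much reassurance a reader may take from agreement between the Investigator and BICR response rates.

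**Working it through.** **Inputs.** The planned evaluable number is 69 (Protocol 10.1, SAP 3.2.2). The ORR rule is SAP 6.1.1.1 and the BICR population is SAP 4.12.3. The number of Investigator-evaluable patients without BICR-measurable disease, k, is not given. It is an assumption, varied here from 1 to 10. I also assume that the BICR set lies inside the 69.

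**The plan's own figures.** None is stated for BICR. The design that supplies the 69 does reproduce by exact binomial calculation (28 then 69 patients, stop at 9 or fewer responders, reject above 26):
- early termination probability 0.7624 (stated 0.762)
- expected sample size 28 + (1 − 0.7624) × 41 = 37.74 (stated 37.74)
- one-sided alpha 0.0245 (stated 0.024)
- power 0.9001 (stated 0.9)

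**Step 1: effect of the denominator.** With R BICR responders, none of them among the k dropped, the SAP rule gives R/(69 − k) and the common set gives R/69. The shift is R·k / [69 × (69 − k)]. With R = 30, the common set gives 30/69 = 43.5% (Clopper-Pearson 95% CI 31.6 to 56.0).

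| k | SAP rule | Shift in points |
|---|---|---|
| 1 | 30/68 = 44.1% | 0.6 |
| 2 | 30/67 = 44.8% | 1.3 |
| 6 | 30/63 = 47.6% | 4.1 |
| 10 | 30/59 = 50.8% | 7.4 |

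**Step 2: effect on the gap between readers.** Assume 33/69 Investigator responders (47.8%). Assume also that all k dropped patients are Investigator responders, and that BICR agrees with the Investigator on everyone else.

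| k | BICR ORR, SAP rule | Gap to 47.8% | BICR ORR, common set | Gap to 47.8% |
|---|---|---|---|---|
| 2 | 31/67 = 46.3% | 1.6 | 31/69 = 44.9% | 2.9 |
| 5 | 28/64 = 43.8% | 4.1 | 28/69 = 40.6% | 7.2 |
| 10 | 23/59 = 39.0% | 8.8 | 23/69 = 33.3% | 14.5 |

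At k = 5, response agreement is 64/64 (100%) among the patients BICR analyses, but 64/69 (92.8%) on the common set.

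**Step 3: a change of patients alone moves the rate.** Suppose instead that the 5 dropped patients are Investigator non-responders and BICR agrees on all the others. The SAP rule gives 33/64 = 51.6%. BICR would then exceed the Investigator's 47.8% by 3.7 points with no disagreement on any response.

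**Step 4: is the direction certain?** No. The overall response table in Protocol Appendix B allows a CR when there are no target lesions and all non-target disease has cleared. Take k = 1, with that patient a BICR CR. Dropping her gives 30/68 = 44.1%. Keeping her as a responder gives 31/69 = 44.9%, so here exclusion lowers the rate. Counting her as a non-responder gives 30/69 = 43.5%.

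**The case against.** The SAP's rule is coherent on its own terms: each reader's response rate is taken over patients that reader found measurable. Protocol Section 10 requires measurable lesions per RECIST v1.1 without naming the assessor, so separate sets can be read as elaboration. The common-set alternative has its own weakness, since it scores a non-target CR as a non-response. These arguments support keeping the BICR-measurable set as a supportive analysis. They do not make it a like-for-like check on the Investigator.

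The documents do not support several stronger readings that a reader might infer.

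- **That the BICR ORR is inflated.** This needs k above zero and dropped patients who would not be BICR responders. Both are plausible; neither is established.
- **That the 75 enrolled versus 69 evaluable gives k = 6.** That allowance is for treated patients who are not efficacy evaluable under the protocol's general definition. It does not estimate BICR non-measurability, and 75 is not the base of the primary ORR.
- **That these patients disappear.** They stay in the primary ORR, and SAP 5.2.2 reports the size of every analysis population. What stays hidden is their Investigator response. A patient with any other BICR-measurable lesion is not dropped.
- **That a decision could flip.** With 27 BICR responders, dropping 2 patients moves the lower 95% limit from 27.6% (27/69) to 28.5% (27/67), across the 28% null. But SAP 4.10 applies that test to the primary endpoint, and SAP 4.11.2 plans no formal test of secondary endpoints.

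Two further points stand. Inclusion criterion 6 requires a measurable lesion, so k may be small. And at 30/69 the interval is about 24 points wide, wider than any shift in Step 1. CA-125 response offers some laboratory-based corroboration, but it does not check scan reading.

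**Conclusion.** The point holds in limited form. SAP 4.12.3, applied through 6.1.1.1 and 6.5, excludes from the BICR ORR every patient with Investigator-measurable but no BICR-measurable disease, and nothing else planned shows how the two readers compare on those patients. The likely effect is a higher BICR ORR and understated discordance; neither is certain.

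The shift is 0.6 to 7.4 points for k from 1 to 10. This rests on an assumed 30 BICR responders, a base of 69, and dropped patients who are all BICR non-responders. The documents do not say where in that range k falls. The primary Investigator test and its conclusion are untouched. This is an inexpensive improvement to a sensitivity analysis and does not undermine the trial's main result.

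**What to change.** 1. In SAP 6.5, report BICR ORR on the Investigator Efficacy Evaluable set used for the primary analysis. Count patients without BICR-measurable disease as non-responders, and flag any with a BICR CR based on non-target disease only.
2. Keep the ORR on the BICR-measurable set as a supportive analysis.
3. Add a patient-level Investigator-by-BICR response table with a separate row for no measurable disease per BICR.
4. List the BICR-specific population in SAP Section 9 as a revision from the protocol.

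SAP 2.1 allows changes before final database lock; after that, the additional analysis would be documented in the study report as a deviation from the SAP. No new data are needed. The cost is one or two extra tables and a BICR ORR that may look less favourable.

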4.12.4. CA-125-Evaluable Population

The CA-125-Evaluable population is defined as all patients in the Safety population whose pretreatment sample is ≥ 2.0 times the upper limit of normal (ULN), within 2 weeks prior to first dose of MIRV, and who have at least 1 post-baseline CA-125 evaluation.

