- ⁿ If a patient discontinues before documentation of PD, a tumor assessment and CA-125 will be assessed at the EOT or 30-Day Follow-up visit, if not performed within the previous 6 weeks. Tumor assessments and CA-125 will continue to be performed every 12 (\pm 3) weeks until PD is documented per RECIST v1.1 or the patient starts new anticancer therapy. Patients who discontinue MIRV for reasons other than PD will continue with tumor assessments until documentation of PD or the start of a new anticancer therapy, whichever comes first. Prior to Week 36 (from C1D1), assessments should occur every 6 weeks (\pm 1 week) as allowed by local requirements but must occur at an interval of no more than 12 weeks. After Week 36, assessment will occur every 12 weeks (\pm 3 weeks) until documentation of PD, death, the start of new anticancer therapy, or patient's withdrawal of consent (whichever occurs first).
- ^o CA-125 will be measured at the time of every tumor assessment (\pm 4 days) (responses will be confirmed according to GCIG criteria [Appendix C](#)).
- ^p All SAEs, and those AEs assessed by the Investigator as at least possibly related to study drug should continue to be followed until they resolve or stabilize, whichever comes first.

Document ID: CLIN-00067	Title: IMGN853-0419 Clinical Study Protocol	Version: 2 . 0
Legacy ID: 26587		Approved Date: 12/22/2021

^q Only AEs/SAEs which are considered related to a study procedure (ie, blood draw or fresh tumor biopsy) will be captured during the Pre-screening period, ie, from the time of signing the Pre-screening consent (if one is utilized) until the signing of the main study informed consent, or until the patient is determined to be a screen failure.

^r Immunogenicity will be assessed in samples collected prior to dosing (predose) on C1D1, C2D1, C3D1, C5D1, at EOT, and 30-Day Follow-up.

^s Survival follow-up assessments will occur every 3 months (± 1 month) until death, the patient is lost to follow-up or withdrawal of consent for survival follow-up, or EOS (whichever comes first). These assessments may be conducted by telephone. Information on the start of new anticancer therapy (including start date, therapy type/name, and response on treatment) should be collected. Additional survival follow-up calls may occur periodically if needed for regulatory requests or at time of database lock for either primary or final analysis.

Document ID: CLIN-00067	Title: IMGN853-0419 Clinical Study Protocol	Version: 2.0

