7.13.2. CA-125

Serum CA-125 assessments will be performed within 14 days prior to the first dose of study drug, and at each radiologic tumor assessment (\pm 4 days) (Table 2). CA-125 should be assessed by the same laboratory throughout the study.

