10.3. Efficacy

Unless stated otherwise in the SAP, efficacy analyses will be performed on the Efficacy Evaluable Population.

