This CA-125 response definition has been produced to evaluate relapse therapy. If assessing therapy that includes 2 treatment modalities for relapse (eg, surgery and chemotherapy), any CA-125 response results from both treatments. CA-125 cannot distinguish between the effects of each treatment. To calculate response rates in protocols, an ITT analysis should be used that includes all patients with an initial CA-125 level of at least twice the ULN as eligible and evaluable. In addition to calculating response rates in protocols, it is advisable to record those patients who have both a CA-125 response and whose CA-125 level falls to within the normal range.

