3.1.3.2. Key Secondary Endpoint

- Duration of response (DOR), defined as the time from initial Investigator-assessed response (CR or PR) until progressive disease (PD) as assessed by the Investigator.

3.1.3.3. Additional Secondary Endpoints:

- Treatment-emergent adverse events (TEAEs) and laboratory test results, physical examination, or vital signs.
- CA-125 response determined using the GCIG criteria defined in [Appendix C](#) of the Protocol.
- Progression-free survival (PFS), defined as the time from first dose of MIRV until Investigator-assessed radiological PD or death, whichever occurs first.
- Overall survival (OS), defined as the time from first dose of MIRV until death.
- ORR, DOR, and PFS by blinded independent central review (BICR) will be summarized as sensitivity analysis.

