6.1.4. GCIG CA-125 Response

A GCIG CA-125 response is defined as a $\geq 50\%$ reduction in CA-125 levels from baseline. The response must be confirmed and maintained for at least 28 days. The CA-125 response will be conducted using the CA-125-Evaluable population. The date of response corresponds to the date when the CA-125 level is first reduced by 50%. The summary table for CA-125 will include the number (percentage) of patients in the CA-125-Evaluable population, and that number will then be used as the denominator for CA-125 response rate. The CA-125-Evaluable population is defined as all patients in the Safety population whose pretreatment sample is ≥ 2.0 times the upper limit of normal (ULN), within 2 weeks prior to first dose of MIRV, and who have at least 1 post-baseline CA-125 evaluation.

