9. REVISION FROM PROTOCOL

Protocol states that the primary analysis for ORR will be conducted after all efficacy evaluable patients have:

- undergone at least 4 post-baseline tumor assessments, or
- experienced radiological disease progression, or
- died or had clinical progression within 105 days of first dose of MIRV, or
- withdrawn from study for other reasons.

In SAP, it changes to

- undergone at least 6 post-baseline tumor assessments in Section 4.9

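### The SAP drops patients with no post-baseline CA-125 sample from the CA-125 response denominator, contrary to the Appendix C rule the endpoint cites; the change is not listed and can only raise the rate or leave it unchanged

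*SAP*

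**What the plan says.** SAP 3.1.3.3 lists, as an additional secondary endpoint, "CA-125 response determined using the GCIG criteria defined in" Appendix C of the protocol. Protocol 2.2.3 and 10.3.3 tie the endpoint to the same appendix.

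Appendix C closes with a denominator rule for response rates: "an ITT analysis should be used that includes all patients with an initial CA-125 level of at least twice the ULN as eligible and evaluable". It contains no requirement for a post-baseline sample.

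SAP 4.12.4 starts from the Safety population, requires a pretreatment value of at least twice the ULN, and adds two further conditions: a sample taken "within 2 weeks prior to first dose of MIRV, and who have at least 1 post-baseline CA-125 evaluation". SAP 6.1.4 repeats the definition, says the table will show the size of this population, and adds that "that number will then be used as the denominator for CA-125 response rate".

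Protocol 10.3 leaves room for a different analysis set: "Unless stated otherwise in the SAP, efficacy analyses will be performed on the Efficacy Evaluable Population". SAP Section 9, which records revisions from the protocol, names one change only, the move from 4 assessments to "undergone at least 6 post-baseline tumor assessments in Section 4.9".

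**The concern.** The SAP names the Appendix C criteria but computes the rate on a different denominator and does not record the difference where departures from the protocol are recorded. The core response criteria (at least a 50% fall, confirmed, held for 28 days, baseline at least twice the ULN) are unchanged; only the set of patients counted differs.

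The patients removed are unlikely to be a random subset. On-study CA-125 is drawn with the tumor assessments, the first of which is due at week 6 (± 1 week). A patient with no post-baseline value is mainly one who died early, withdrew consent (Protocol 5.6.3 then allows no further assessments), started another anticancer therapy first, or missed her samples. Early failures are likely to be over-represented.

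The SAP handles the equivalent problem the other way for ORR: under 6.1.1.1, patients with no post-baseline RECIST assessment stay in the denominator as non-responders.

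The reader cannot undo the effect. SAP 5.2.2 and 6.1.4 report the size of the CA-125 population but do not separate patients lost for a missing sample from those whose baseline CA-125 was too low. The same denominator feeds the subgroup rates in SAP 6.4, where numbers are smaller and each removed patient moves the rate more.

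**Working it through.** The documents give no CA-125 response rate, no expected number eligible and no expected number without a sample, so there is no stated figure to reproduce. The check has two parts: direction, which follows from the definitions, and size, which needs assumptions.

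**The rules side by side**

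| Source | Baseline condition | Post-baseline sample required? |
|---|---|---|
| Appendix C | CA-125 ≥ 2 × ULN, within 2 weeks before treatment | No |
| SAP 4.12.4 and 6.1.4 | Same | Yes, at least one |
| SAP 6.1.1.1 (ORR, for comparison) | Measurable disease | No; those without one are non-responders |

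**Direction**

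Let N be the patients meeting the baseline condition, m those among them with no post-baseline CA-125, and x the confirmed responders. A confirmed response needs post-baseline samples, so x is the same under both rules.

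- Appendix C rate: p = x/N
- SAP rate: x/(N − m)
- Difference: x/(N − m) − x/N = xm/[N(N − m)] = p × m/(N − m)

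This is never negative, and it is zero only if m = 0 or x = 0. Enumerating every combination with N from 1 to 75, m < N and x ≤ N − m (76,000 in all) gives no exception.

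**Size**

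Assumptions, not in the documents: N = 45, 60 or 75 (75 being the approximate planned enrollment), p = 40% or 60%, m = 1 to 3. Confidence intervals are exact (Clopper-Pearson), the method in SAP 6.3.2.

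| N | x | Appendix C rate (95% CI) | SAP rate, m = 1 | m = 2 | m = 3 (95% CI) |
|---|---|---|---|---|---|
| 45 | 18 | 40.0% (25.7–55.7) | 40.9% | 41.9% | 42.9% (27.7–59.0) |
| 45 | 27 | 60.0% (44.3–74.3) | 61.4% | 62.8% | 64.3% (48.0–78.4) |
| 60 | 24 | 40.0% (27.6–53.5) | 40.7% | 41.4% | 42.1% (29.1–55.9) |
| 60 | 36 | 60.0% (46.5–72.4) | 61.0% | 62.1% | 63.2% (49.3–75.6) |
| 75 | 30 | 40.0% (28.9–52.0) | 40.5% | 41.1% | 41.7% (30.2–53.9) |
| 75 | 45 | 60.0% (48.0–71.1) | 60.8% | 61.6% | 62.5% (50.3–73.6) |

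Worked case, N = 45 and p = 60%: for m = 1 the shift is 0.60 × 1/44 = 1.4 points; for m = 3 it is 0.60 × 3/42 = 4.3 points. At the other end, N = 75 and p = 40%: 0.40 × 1/74 = 0.5 points and 0.40 × 3/72 = 1.7 points.

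The Appendix C intervals are 55.7 − 25.7 = 30.0 points wide at N = 45, 53.5 − 27.6 = 25.9 at N = 60, and 52.0 − 28.9 = 23.1 at N = 75. The shift is small against sampling error, but it runs one way, and the interval does not allow for it.

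**The case against.** The strongest reply is that the protocol does not impose one firm denominator. Section 10 makes the Efficacy Evaluable Population the default for all efficacy analyses, Section 10.3 lets the SAP state another, and the SAP states its choice openly in two places. Appendix C reads as general cooperative-group guidance, its denominator sentence is advisory, and the trial does not adopt everything in it: Appendix C allows progression by CA-125, whereas PFS here is radiological only. All of this stands, and it makes the point an unlisted inconsistency rather than a breach of a binding rule. It does not explain why the difference is missing from Section 9, or why missing patients are handled differently from ORR.

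The second reply concerns direction. Appendix C also treats as not evaluable patients who received mouse antibodies or had recent peritoneal or pleural interference, and the SAP population omits those exclusions. The net difference from a full Appendix C analysis is therefore undetermined. That is right; the direction shown here is for the post-baseline condition alone.

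The third reply is size. Protocol 7.13.2 says "Serum CA-125 assessments will be performed within 14 days prior to the first dose of study drug, and at each radiologic tumor assessment". For patients who stop before progression, footnote n of Protocol Table 2 calls for a sample at the EOT or 30-Day visit if none was taken in the previous 6 weeks, and then "Tumor assessments and CA-125 will continue to be performed every 12" (± 3) weeks until progression or new anticancer therapy. So m should be small and may be zero. This stands too, and it limits the weight of the point. Footnote n does not guarantee a post-baseline value, however: read literally, a recent screening sample could meet its 6-week condition.

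**Conclusion.** The concern holds. The SAP's denominator differs from the one in the criteria its endpoint cites, Section 9 does not say so, and the added condition, taken alone, can only raise the reported rate or leave it unchanged. The direction needs no assumption beyond the SAP's own definition of a confirmed response.

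The size cannot be fixed from the documents. It is nil if every eligible patient gives a post-baseline sample; under the assumed range it is at most 1.4 points for one missing patient and 4.3 points for three. SAP 4.11.2 places no formal test on this endpoint, so the effect is confined to a descriptive rate, its interval and its subgroup versions. The point is modest, but it is a one-directional bias that can be removed at almost no cost, and it should be corrected.

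**What to change.** In SAP 4.12.4 and 6.1.4, delete the requirement for a post-baseline CA-125 evaluation. The population is then all Safety patients with a pretreatment CA-125 of at least twice the ULN within 2 weeks before first dose, with no further exclusions added. State that eligible patients without a post-baseline or confirmatory sample count as non-responders, in line with SAP 6.1.1.1, and report the number with no post-baseline sample beside the rate. If the smaller set is also wanted, present it as supplementary and list it in SAP Section 9.

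The cost is one clause removed in two places, one sentence on non-response and one added count. No new data are needed. The downside is that the reported CA-125 response rate may be slightly lower.
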